4.2. Scientific Rationale for Study Design

The general rationale for the study design is described in Section 2.1.

4.3. Doses and Justification for Doses

The Phase 1 study (ADSPAM) conducted by Baylor College of Medicine has cleared five dose cohorts to date: 5 x 10⁶ cells/m² (DL1); 10 x 10⁶ cells/m² (DL2); 20 x 10⁶ cells/m² (DL3); 50 x 10⁶ cells/m² (DL4) and 100 x 10⁶ cells/m² (DL5) (see Section 2.2.6 for a detailed description). Based on data gathered by Baylor, Marker has considered DL3, DL4 and DL5 safe to proceed with and has proposed the dosing schema for the Phase 2 study that is described in detail under the respective sections below.

In summary, for the Safety Lead-in portion, which was included for the purpose of comparing MT-401 manufactured with peptides produced from two different vendors, Marker proposed a flat dose of 50×10^6 cells, which is equivalent to 20×10^6 cells/m² (DL3 of the Phase 1 study) for ease of comparison. For the main portion of the Phase 2 study, Marker proposed a flat dose of 100×10^6 million cells, which is equivalent to 50×10^6 cells/m² (DL4 of Phase 1 study).

Part 2 of the study includes Cohorts III, IV and V which will run in parallel with Phase 2. Cohort III will evaluate MT-401 at a higher dose (200×10^6 million cells) than the dose used in the Phase 2 portion using the current manufacturing process. If Cohort III data determines the 200×10^6 cell dose to be safe, the Phase 2 patients may be switched to receive 200×10^6 cell dose, infused three times at intervals of at least 2 weeks. Cohorts IV and V will evaluate MT-401 manufactured using an accelerated manufacturing process at 100 and 200×10^6 cell doses, respectively. Following completion of Cohorts IV and V, the

Confidential Page 30 of 74

Sponsor may change the Phase 2 dose to the dose deemed to be safe for MT-401 manufactured using the accelerated process.

A total of 15-30 patients (3-6 patients per cohort) will be treated in Cohorts I-V. The dosing schemes are shown in Table 4.

Table 4: **Dosing Scheme**

Cohort		MT-401 dose	Number of Patients	Peptide Manufacturer
	Level			
-I	-1	25 x 10 ⁶ cells flat dose	3-6 patients	JPT
-II	-1	25 x 10 ⁶ cells flat dose	3-6 patients	Almac
I	1	50 x 10 ⁶ cells flat dose	3-6 patients	JPT
II	1	50 x 10 ⁶ cells flat dose	3-6 patients	Almac
III	3	200 x 10 ⁶ cells flat dose	3-6 patients	Almac ^a
-IV	1	50 x 10 ⁶ cells flat dose	3-6 patients	Almac
IV^b	2	100 x 106 cells flat dose	3-6 patients	Almac a
V^b	3	200 x 10 ⁶ cells flat dose	3-6 patients	Almac ^a

^a Almac is the preferred manufacturer if both JPT and Almac are deemed to be safe during evaluation of Cohorts I and II of the Safety Lead-in portion. ^b MT-401 product manufactured using an accelerated process

4.3.1. Safety Lead-in Portion of the Phase 2 Study

The Safety Lead-in portion includes two cohorts (Cohort I and Cohort II) that will evaluate the safety profiles of MT-401 manufactured with peptide pools obtained from two different vendors (JPT versus Almac). Therefore, Cohorts I and II may be enrolled in parallel. Approximately 3-6 patients closely fitting the eligibility criteria of active disease (Group 2) will be infused with MT-401 in each of Cohorts I and II to determine the safety of patient-specific product consisting of 50 x 10⁶ cells (flat dosing) every 2 weeks for a total of 3 doses using the standard 3+3 design (Section 4.5). A minus 1 (-1) dose level of 25 x 106 cells (flat dosing) may be used should the need arise to de-escalate (Section 4.3). All patients treated will be observed for 28 days from the day of the initial MT-401 infusion before safety is established. If no differences in the safety are noted between the peptide vendors, then it will be concluded that the change in peptide manufacturer is not relevant to dosing and the main portion of the Phase 2 study will be initiated with the product utilizing Almac peptides.

4.3.2. Main Portion of the Phase 2 Study

Following completion of the Safety Lead-in portion the study will proceed to open Groups 1 and/or 2 of the Phase 2 study at the highest cleared dose of 100×10^6 cells (DL4 – 50×10^6 cells/m²) from the Phase 1 trial. Briefly, in the dose escalation portion of the Phase 1 ADSPAM study, 50 x 10⁶ cells/m² cohort (DL4 - 100 x 106 cells) completed evaluation with 2 patients, and neither patient had any DLTs noted. A 100 x 10⁶ cells/m² dose cohort (DL5 – 200 x 10⁶ cells) has completed the DLT period for 1 patient without any DLTs noted. Therefore, patients in Groups 1 and 2 will receive three consecutive flat doses of 100 x 10⁶ cells every 2 weeks. MT-401 will be given by IV infusion through either a peripheral or central line. The patients will be monitored for any safety concerns for 1 hour after infusion as outpatients.

In total, approximately 210 patients will be treated in the Phase 2 portion of the study. The Phase 2 portion includes two groups of patients who will be treated with product as adjuvant therapy (Group 1) or

Confidential Page 31 of 74

with active disease (Group 2). Approximately 150 patients will be randomized 1:1 to either MT-401 product or standard of care therapy in Group 1 (adjuvant) and 60 patients with active disease will be treated in Group 2.

Following completion of Cohorts I and II, the confirmed peptide manufacturer to be used in Phase 2 will be identified based on review of the safety data. At any time, following completion of Cohort III the Sponsor may change the Phase 2 dosing regimen to that evaluated in Cohort III. At the conclusion of Cohorts IV and V, which evaluate the safety of the product manufactured using an accelerated process at two different doses, the Sponsor may change the Phase 2 dose to the dose deemed to be safe for MT-401 manufactured using the accelerated process.

4.3.3. Cohort III: 200 x 10⁶ cells

In parallel to the opening of Groups 1 and/or 2, a separate cohort (Cohort III) will test DL5 being studied in the Phase 1 trial, which is the flat dose equivalent of 200×10^6 cells. Three to 6 patients will be dosed to determine the safety of this dose level using the standard 3+3 design (see Section 4.5). If the 200×10^6 cells dose being tested in Cohort III is noted to be safe, then the patients enrolled, but not yet treated, in Groups 1 and 2 may be treated at the 200×10^6 cells dose, unless the Sponsor decides to remain at the current dose of 100×10^6 cells.

4.3.4. Cohorts IV and V

Cohorts IV and V will evaluate the safety of MT-401 manufactured using the accelerated method at doses of 100×10^6 and 200×10^6 cells, respectively. A lower dose level of 50×10^6 cells (flat dosing) may be used should the need arise to de-escalate (Section 4.3). Three to 6 patients will be dosed in each cohort to determine the safety and tolerability using the standard 3+3 design (Section 4.5). Patients enrolled, but not yet treated, in Groups 1 and 2 may be treated with this MT-401 product at the initial Phase 2 dose of 100×10^6 cells or higher at 200×10^6 cells.

For additional details on administration, please refer to the Investigational Product Manual.

For allowable dose modifications, please refer to Section 6.6.

4.4. Study Period and End of Study Definitions

Screening: begins when the informed consent form (ICF) is first signed. The patient is enrolled once Screening tests have been completed successfully and prior to HSCT for Group 1 patients, and prior to the start of manufacturing for Group 2 patients.

Baseline: A re-assessment of eligibility will occur within 14 days prior to group assignment for Group 1 to confirm eligibility has been met.

Randomization: Randomization to MT-401 or SoC for patients in Group 1 will occur once eligibility has been reconfirmed post-HSCT and groups have been assigned.

Study Period: begins the day of the first patient's first dose of MT-401 and ends at End of Study.

Confidential Page 32 of 74

- Study Treatment Period: begins with the day of the patient's first study treatment and ends the day the patient and investigator agree that the patient will discontinue study treatment or after all doses of MT-401 have been administered (whichever is earlier) (including for the Safety Lead-in portion of the study).
- Follow-up Period: begins the day after the study treatment period ends and is complete the day of the patient's death, withdrawal of consent, loss-to-follow-up or End of Study (whichever is earlier). It includes safety follow-up visits and additional long-term follow-up visits, as outlined in the SoA (Table 1):
 - Active Follow-up: occurs after the last dose of MT-401 has been administered until
 patient relapses/progresses or declines any additional study visits (but patient may
 continue with survival follow-up).
 - Survival Follow-up: begins the day a patient relapses as determined by investigator or declines any additional study visits and ends with the End of Study.

End of Study: A patient is considered to have completed the study if he/she has completed the planned study treatment and follow-up periods of the study as per SoA, withdrawn, patient's death or lost to follow-up.

No intervention following the End of Study is planned, and patients will return to their physician for further management.

4.5. 3+3 Design (Safety Lead-in and Cohorts III-V)

A minimum of 3 patients each will be treated in Cohorts I and II; if 1 patient experiences a DLT related to MT-401, 3 additional patients will be treated in the cohort (see Section 5.6). If overall, 0 out of 3 patients or 1 out of 6 patients experience a DLT in the specific cohort, this dose will be established as safe for the Phase 2 portion of the study (see Section 5.6). Additional patients may be treated to acquire data such as biomarkers as long as no safety issues arise. In the event that > 1 patient, experiences a DLT (see Section 5.6) related to MT-401, then no further patients will be treated in that cohort. A new cohort of patients will be treated at a lower dose level (DL1) with a flat dose of 25 x 10⁶ cells (Cohorts -I or -II). Dose Level 1 will be repeated with an additional 3-6 patients once new peptides are synthesized for use during manufacturing (Cohort II). If Cohort II is deemed safe for patients, this dose and peptide manufacturer will be used in the Phase 2 portion of the study. In parallel to opening the Phase 2 portion of the study, Cohorts III-V will open to enroll patients using the same standard 3+3 design described above for Cohorts I and II.

Patients who initially receive any dose of MT-401, but are subsequently deemed unevaluable (e.g., important protocol deviation, starting investigational drugs not approved by the Sponsor) and removed from the study will not count as DLTs in the Safety Lead-in and Cohorts III-V and may need to be replaced.

Confidential Page 33 of 74

5. STUDY POPULATION

Prospective approval of protocol deviations to recruitment and enrollment criteria, also known as protocol waivers or exemptions, is not permitted.

5.1. Patient Inclusion Criteria

All applicable inclusion and exclusion criteria must be met at Screening (up to 28 days before allogeneic HSCT for Group 1 patients, and prior to the start of manufacturing for Group 2 patients, or at the time of consideration for study) and at Baseline (re-assessment of eligibility within 14 days prior to group assignment for Group 1).

Patients are eligible to be included in the study only if all of the following criteria apply and the patient, in the judgement of the investigator, is an appropriate candidate for experimental therapy:

- 2. Eligible to receive donor-derived MT-401 following first allogeneic HSCT, are in ≤ third complete remission (CR3) prior to transplant (including matched sibling, matched unrelated donor with at least 6 of 8 HLA markers, or haploidentical with at least 5 of 10 HLA markers) as:
 - Adjuvant therapy for AML (**Group 1**) at 85-130 days post-HSCT defined as:
 - patients with CR_{MRD}- by central testing for purposes of randomization (if optional local MRD testing performed and results are positive, the patient will be moved to Group 2 subgroup D);
 - and are considered intermediate/high risk (e.g., pre-transplant MRD+, intermediate/adverse risk cytogenetics or received non-myeloablative or reduced intensity conditioning); or
 - Treatment for relapsed AML (first relapse post-HSCT) when disease occurs after transplant (Group 2) defined as
 - First relapse (MRD+ or frank relapse) post-HSCT
 - Patients in Group 1 who are randomized to Arm B (SoC) and experience first relapse (MRD⁺ or frank relapse) post-HSCT or experience relapse prior to randomization
 - Patients with frank relapse will enter into Subgroup C while patients with MRD⁺ disease will enter into Subgroup D
 - Safety Lead-in (Cohorts I and II) and Cohorts III-V defined as patients whose prior treatment course does not meet precise eligibility criteria but may still be approved upon review by the Sponsor as described above for Group 2 only

Note: Engraftment must be confirmed post-transplant (absolute neutrophil count $> 1000/\text{m}^3$ without granulocyte colony-stimulating factor for 7 days, donor chimerism $\ge 50\%$).

- 2. Are ≥18 years of age prior to administration of MT-401
- 3. Patients must have donor-derived cells available to make MT-401

Confidential Page 34 of 74

- 4. Karnofsky/Lansky score of ≥60
- 5. Life expectancy ≥ 12 weeks
- 6. Adequate blood, liver, and renal function
 - Blood: Hemoglobin \geq 7.0 g/dL (can be transfused)
 - Liver: Bilirubin ≤1.5X upper limit of normal; aspartate aminotransferase ≤3X upper limit of normal
 - Renal: Serum creatinine ≤2X upper limit of normal or measured or calculated creatinine clearance >45mL/min
- 7. Sexually active patients must be willing to utilize one of the highly effective birth control methods or practice complete abstinence starting from Screening for T cell infusion until 6 months after the last T cell infusion (see details in Section 8.3.5). Male patients who are sexually active must agree to use a condom during this period.
- 8. Patients are allowed to be on experimental conditioning regimens prior to transplant if no planned maintenance therapy post-transplant.
- 9. In Group 2, patients may receive bridging therapy at the investigators' discretion in situations where MT-401 is not ready for administration or the treating physician believes the patient would benefit (particularly in cases of high tumor burden) for ≤6 months as long as the following criteria are met:
 - Disease assessment including bone marrow biopsy to be performed within 14 days prior to administration of MT-401 (patients may receive MT-401 even if CR MRD is achieved post-bridging therapy but will be analyzed separately; additionally, patients must have ≤30% bone marrow blasts)
 - At least 4 half-lives or 1 week has passed after administration of bridging therapy whichever is shorter

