1.3. MT-401 Schedule of Activities

Table 1: Schedule of Activities

Procedure	Screening a	Baselineb	Intervention Period and Follow-up [Weeks] ^c						
			0 ^d	2 ^d	4 ^d	Follow-up	Visits ^e		
						12 (±1 week	24 (±1 week	52 (±4 weeks)	Yearly (±4 weeks)
Informed consent	X	X							
Inclusion and exclusion criteria	X	X							
Demography	X								
Medical History and Complete Physical Exam (includes performance status)	X	X							
Brief Physical Exam ^f			X	X	X	X	X	X	X
Pregnancy test (WOCBP only) (serum or urine) ^g	X	X							1
Laboratory assessmentsh	X	X	X	X	X	X	X	X	X
Vital signs ⁱ	X	X	X	X	X	X	X	X	X
Randomization for Group 1 patients ^b		X							
Disease Assessment	X	X	X^k			X	X	X	X
GVHD Assessments		X	X	X	X	X	X	X	X
Study treatment			X	X	X				
AE, SAE, and concomitant medication review		X	X	X	X	←		•	
Biomarkers ⁿ			X			X	X	X	X
PRO questionnaire (Group 2 Subgroup C only) ^o	X	X				X	X	X	X

Abbreviations: AE=adverse event; CBC=complete blood count; eCRF=electronic case report form; GVHD=graft-versus-host disease; HSCT=hematopoietic stem cell transplant; MRD=minimal residual disease; PRO=patient-reported outcome; SAE=serious adverse event; SoA=Schedule of Activities; SoC=standard of care; WOCBP=women of childbearing potential Note: Additionally, treatment visits may be modified for 1 week due to inclement weather, vacation, etc., but any longer durations need to be discussed with the Sponsor. Any unscheduled visit, including discontinuation visits, will follow the assessments shown for Week 24.

Page 18 of 74

^a Screening is to be performed up to 45 days before allogeneic-HSCT or at the time of consideration for study.

^b Baseline for Group 2 patients should be performed within 14 days prior to first infusion. Disease assessment occurs at Day 80 (±5 days) post-HCST, prior to randomization for Group 1 patients.

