^j Disease assessment will be performed on blood, bone marrow samples, and/or other tissue samples at these time-points. For Group 1 and Group 2, the screening disease assessment may be performed as part of SoC (prior to consent if it was already completed). For Group 1, pre-transplant testing of MRD should be performed locally by any testing methodology and results recorded in the eCRF. Post-transplant baseline MRD testing will be performed centrally, and results must be available prior to randomization. If any additional disease assessments, such as additional time points or additional testing (e.g., imaging for extramedullary disease), or visits occur due to clinical necessity, information will be recorded on eCRF. Includes central testing for MRD status for all samples collected as per SoC and as per standard institutional guidelines at other time points by methods outlined in protocol in Section 4.1 (samples stored for central confirmation at later date). If imaging is performed on a patient, the Sponsor may request imaging to be sent to a central vendor along with any disease assessment reports.

Disease assessment at Day 0 for Group 1 only (disease assessment does not need to be repeated if within 3 weeks of prior disease assessment and results can be pending prior to treatment).

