Study treatment is administered for all patients (except SoC - Group 1- Arm B) on Day 0 and every 2 weeks for a planned maximum of 3 doses. Patients randomized to SoC (Group 1B) at 80 days post-transplant may crossover to the relapse group (Group 2) if the patient is found to have relapse of disease (MRD* or frank relapse) and the subgroup is open and/or Sponsor agreement. After relapse and prior to bridging chemotherapy, the patient should perform assessments associated with the Screening visit if not already completed. The patient should perform the assessments associated with Baseline following bridging chemotherapy and prior to MT-401 administration. The patient will have their visits reset and have their MT-401 administered on Day 0 and follow the schedule of events from that point forward. Group 1- Arm B (SoC) patients will continue to follow the SoA minus administration of MT-401. Refer to Section 6 for additional dosing details. Administration of MT-401 can be delayed due to management of AEs or other toxicities, but patients should resume T cell infusions within 2 weeks of their scheduled dose. If greater than 2 weeks is needed, Sponsor will determine if patient can resume T cells infusions.

m All AEs and SAEs, from Day 0 and Baseline, respectively, to the Week 12 Visit will be collected; after Week 12, only treatment-related AEs and SAEs will be collected.

ⁿ Detailed studies outlined in Section 8.8.

o Additional details regarding the PRO questionnaire and associated instructions will be provided in a separate document.

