3. OBJECTIVES AND ENDPOINTS

Table 3: Objectives and Endpoints

Phase	Objectives	Endpoint
	Primary	
Sa fety Lead-in (Cohort I and II) & Cohorts III-V	 To assess sa fety and tolerability of MT-401: Manufactured using peptides produced by two different vendors (Safety Lead-in: Cohorts I and II). At a higher dose than the dose used in the Phase 2 portion of the study (Cohort III). Manufactured using an accelerated manufacturing process at two dose levels (Cohort IV and V) 	DLTs Sa fety (including but not limited to): TEAEs, SAEs, deaths and clinical laboratory abnormalities per National Cancer Institute (NCI) Common Terminology Criteria for Adverse Events (CTCAE, Version 5.0)
Phase 2 - Adjuvant (Group 1)	To compare relapse-free survival (RFS) for MT-401 (Arm A) vs standard of care (SoC; Arm B)	RFS

Confidential Page 26 of 74

Phase	Objectives	Endpoint
Phase 2 – Active Disease (Group 2):	 Subgroup C (frank relapse): to estimate complete remission (CR) rate and duration of CR (DOCR) Subgroup D (MRD⁺): to estimate complete remission (CR_{MRD}-) rate and duration of CR without minimal residual disease (DOCR_{MRD}-) 	 Subgroup C: CR rate DOCR Subgroup D: CR_{MRD}-rate DOCR_{MRD}-
	Secondary (Efficacy)	
Sa fety Lead-in (Cohorts I and II) & Cohorts III-V	 To assess efficacy of MT-401: Manufactured using peptides produced by two different vendors (Safety Lead-in: Cohorts I and II). At a higher dose than the dose used in the Phase 2 portion of the study (Cohort III). Manufactured using an accelerated manufacturing process at two dose levels (Cohort IV and V) 	CR rate and DOCR (Active disease patients)
Phase 2 (Adjuvant-Group 1)	 To analyze overall survival (OS) for MT-401 (Arm A) and SoC (Arm B) To compare graft-versus-host disease RFS (GRFS) for MT-401 (Arm A) vs SoC (Arm B) 	• OS • GRFS
Phase 2 (Active Disease- Group 2: Subgroups C and D)	 To evaluate overall response rate (ORR), duration of response (DOR), progression-free survival (PFS) and OS for MT-401 alone To evaluate RFS, OS, and GRFS for patients who achieve CR following bridging therapy 	ORRDORPFSOSRFSGRFS
	Secondary (Safety)	
Phase 2 (Adjuvant-Group 1 and Active Disease- Group 2)	To evaluate the safety and tolerability of administering donor-derived MT-401 to patients with AML post-HSCT	 GVHD Assessments Vital signs Clinical laboratory assessments Physical examination AEs
	Exploratory	

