- CR: For Subgroup C, CR is defined as the proportion of patients who achieve a best response of CR_{MRD-} or CR using the ELN recommendations. For Subgroup D, CR rate is defined as the proportion of treated patients who achieve a best response of CR_{MRD-}. Best overall response (BOR) is defined as the best response designation recorded between the date of first dose and the date of objectively documented relapse per ELN recommendations or the date of subsequent therapy, whichever occurs first. For patients without documented relapse or subsequent therapy, all available response designations will contribute to the BOR assessment.
 - The incidence of converting MRD+ to MRD- was chosen as the primary endpoint for Subgroup D based on the following rational: (1) 2017 ELN recommendations (Döhner et al, 2017) introduced a new response category of CR MRD- recognizing MRD assessment provides a more reliable predictor of outcome than morphological assessment and MRD status has been consistently shown to be an independent prognostic marker for disease outcome (Short et al, 2020; Schuurhuis et al, 2018). (2) Given the nature of single arm design, a binary endpoint was considered a more appropriate primary endpoint than a time to event endpoint such as RFS or OS.
- DOCR: For Subgroup C, DOCR is defined as the time between the date of first documented response of CR_{MRD-} or CR to the date of the first documented relapse per ELN recommendations or death due to any cause, whichever occurs first. For Group 2 Subgroup D, duration of complete response is defined as the time between the date of first documented response of CR_{MRD-} to the date of the first documented relapse per ELN recommendations or death due to any cause, whichever occurs first. For patients who neither relapse nor die prior to analysis cutoff or the start of new anti-cancer therapy, DOCR will be censored on the date of their last evaluable disease assessment on or after the assessment of first documented CR and prior to analysis cutoff or start of new therapy.

6.4.1.3 *Secondary Efficacy Variables*

Safety Lead-in (Cohorts I and II) and Cohorts III-V:

- CR (Active disease patients): defined as above for Group 2
- DOCR (Active disease patients): defined as above for Group 2

Phase 2 Adjuvant (Group 1):

- OS: defined as the time between the date of randomization and the date of death. A patient who has not died will be censored on their last contact date (“last known alive date”).

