Phase 2 Active Disease (Group 2):

The statistical methods for analyzing ORR for Group 2 are identical to those described for CR. For Group 2 active disease patients, DOR, PFS and OS will be estimated using the KM product limit method and summarized similar to RFS for Group 1 as described above. For Group 2 patients achieving CR following bridging therapy, RFS and GRFS will also be estimated using the KM product limit method as described above for Group 1.

7.4.6 *Additional Efficacy Endpoint Analysis Methods*

The analysis of markers of immune function, cell targeting, and signaling pathways will not be discussed in this SAP. If analyses of these endpoint are explored, they will be described in a separate analysis plan and may not be included in the primary CSR.

For Group 1 adjuvant patients, the time to MRD⁺ will be summarized similar to RFS, but with no statistical comparisons.

For Group 2 CR patients, the time to MRD⁻ will be summarized descriptively.

For Group 2 Subgroup D, among patients who had PCR detection of MRD at baseline, the percentage reduction from baseline will be summarized, as well as the number and percentage of patients whose disease level reduced by 50% or more.

A summary of PRO data will be presented using descriptive statistics for Group 2 only.

7.4.7 *Statistical/Analytical Issues*

7.4.7.1 *Adjustments for Covariates*

The planned primary analysis models will include adjustments for stratification factors of pre-transplant MRD status and cytogenetic risk. Subgroup analysis and/or analyses including additional factors may be conducted based on, but not limited to, the following covariates:

- Age (18-64 years, 65 years and above)
- Genetic mutations
- Transplant donor type (matched sibling, matched unrelated, haploidentical)
- Conditioning regimen (myeloablative, reduced intensity/nonmyeloablative)
- Complete remission status prior to transplant (CR1, CR2, CR3)

For time to event endpoints forest plots of the event-free rates at landmark times may be generated to display the outcomes in subgroups. Additionally, Kaplan-Meier plots with subgroup KM curves overlaid on the same plot may be presented. For binary endpoints, the rates within subgroups may be presented in forest plots.

Subgroup analyses are described in Section 7.4.7.7. In addition, data may be analyzed post-hoc to explore the effects of various factors. Such analyses will be labeled as post-hoc.

7.4.7.2 *Handling of Dropouts or Missing Data*

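### For Group 2 patients other than Arm B crossovers, a remission produced by bridging therapy can be first recorded after dose 1 and counted in the CR rate, and no committed analysis would show it

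*Protocol*

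**What the plan says.** Protocol 5.1 sets two conditions for a bridged Group 2 patient. One concerns the marrow: "Disease assessment including bone marrow biopsy to be performed within 14 days prior to administration of MT-401". The other concerns the interval before MT-401: "At least 4 half-lives or 1 week has passed after administration of bridging therapy whichever is shorter". Schedule of Activities footnote b gives the same 14 days, again with no order relative to bridging: "Baseline for Group 2 patients should be performed within 14 days prior to first infusion".

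The order is written down once, in the Schedule of Activities footnote on study treatment, in the text on Arm B patients who cross over: "The patient should perform the assessments associated with Baseline following bridging chemotherapy and prior to MT-401 administration".

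No later pre-dose check exists for Group 2, because of the footnote "Disease assessment at Day 0 for Group 1 only". The next scheduled Group 2 disease assessment is Week 12. SAP 7.1.5 takes the last value before the first dose as the Group 2 baseline, without reference to the end of bridging.

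The response window opens at dose 1 in both Protocol 9.3.3 and SAP 6.4.1.2: "Best overall response (BOR) is defined as the best response designation recorded between the date of first dose".

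The plan does separate some bridging remissions. Protocol 5.1 and 9.1.2 and SAP 7.6 say that patients in CR without MRD after bridging are analysed separately, and 9.1.2 and 7.6 also leave them out of the 60. The protocol synopsis widens the separate analysis to any CR.

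**The concern.** The separate analysis of post-bridging remissions shows that the sponsor does not want them read as MT-401 responses. That safeguard works only if a marrow is taken after bridging has had its effect. Where the marrow may come before the last bridging dose, a patient can enter as active disease, go into remission because of bridging, and be recorded as a responder at the first post-dose assessment.

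At stake are the Group 2 primary CR rate and, in Subgroup C, ORR. Both come from a single-arm group of 30 per subgroup and are read against historical rates, so no concurrent control would reveal the misattribution. No analysis in the SAP is committed to showing it either. SAP 7.4.2 tabulates bridging (yes/no) as a baseline characteristic, but the factors named in SAP 7.4.7.1 end with "Complete remission status prior to transplant (CR1, CR2, CR3") and do not include bridging.

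**Working it through.** **1. Can the marrow come first?** Inputs, all from Protocol 5.1: marrow on Day -14 at the earliest; last bridging dose on Day -7 at the latest when the one-week limit applies, and later when 4 half-lives is shorter.

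Largest compliant lead of marrow over last bridging dose = 14 - 7 = 7 days. For an agent with a very short half-life it approaches 14 days.

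Illustration: marrow on Day -14 shows 12% blasts, bridging ends on Day -7, MT-401 is given on Day 0, and Week 12 shows CR. Both 5.1 conditions are met, and the CR falls inside the response window. Had the marrow been taken on Day -1 and shown CR without MRD, the patient would have been analysed separately.

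**2. Which patients?** Arm B crossovers are covered by the footnote that puts Baseline after bridging. No equivalent sentence covers patients who relapse before randomization or who enter at first relapse after transplant (Protocol 4.1).

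**3. A second route, in Subgroup C only.** The body of the protocol carves out CR without MRD, while Subgroup C counts CR with MRD positive or unknown as a response (Table 6 and 9.3.3). A Subgroup C patient in such a CR after bridging falls outside the body's carve-out even with a well-timed marrow, but inside the synopsis version. In Subgroup D only conversion to CR without MRD counts, so this route does not arise.

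**4. Effect per patient.** With n = 30 per subgroup (Protocol 9.1.2):

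- 1/30 = 3.3 points
- 3/30 = 10.0 points
- 5/30 = 16.7 points

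Three to five misattributed remissions therefore span the 10-15 point threshold.

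**5. The plan's own table, then the effect on it.** Protocol Table 7 (SAP Table 3) uses a one-sided exact test at 0.05. Take r as the smallest count with P(X >= r | 30, p0) <= 0.05, then solve for the rate giving 80% or 90% power:

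| Historical p0 | r | Rate for 80% / 90% power, recomputed | Stated |
|---|---|---|---|
| 10% | 7 | 28.7% / 32.5% | 29% / 32% |
| 20% | 11 | 42.6% / 46.6% | 43% / 47% |
| 40% | 17 | 62.4% / 66.2% | 63% / 66% |

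The table reproduces within 1 point.

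Now assume that MT-401 adds nothing beyond p0, and that a fraction m of the patients who would not otherwise respond have a bridging remission scored as a response. The response probability becomes p0 + (1 - p0) x m. For p0 = 10% and m = 6.7% this is 0.10 + 0.90 x 0.067 = 0.16. The chance of reaching r is then:

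| p0 | m = 0 | m = 3.3% | m = 6.7% | m = 10% |
|---|---|---|---|---|
| 10% | 2.6% | 8.6% | 19.4% | 34.0% |
| 20% | 2.6% | 5.9% | 11.4% | 19.4% |
| 40% | 4.8% | 7.5% | 11.3% | 16.1% |

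The values of m are assumptions, as is the premise that these remissions come on top of the historical rate. The documents give no bridging frequency, no remission rate from bridging and no marrow timing.

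**The case against.** The strongest reply is that the intended order is already clear. The 14-day marrow is a condition placed on bridged patients, and the clause on remission after bridging makes sense only if that marrow reads status after bridging. The crossover footnote says so outright. This stands as evidence of intent. It does not close the gap, because a site following 5.1 and footnote b to the letter can still take the marrow first.

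SAP 7.4.7.1 and 7.4.7.7 describe their subgroup factors as not exhaustive, so a bridging analysis is permitted. That also stands. What is missing is a commitment to do it.

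A reader might infer that every bridging remission is scored as an MT-401 response. The documents do not support that. Crossovers are covered, and CR without MRD seen on a post-bridging marrow is separated.

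A reader might also take "progression-free survival (PFS) and OS for MT-401 alone" as describing the primary CR rate. In Protocol Section 3 that phrase belongs to the secondary objective on ORR, DOR, PFS and OS. The primary objective is to estimate the CR rate and its duration, without that qualifier.

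Finally, one could multiply assumed shares: bridged, marrow too early, remission from bridging. For example, 0.30 x 0.20 x 0.10 = 0.6 points, and 0.70 x 0.50 x 0.30 = 10.5 points. None of these shares is documented. The product also ignores that, unless an unscheduled assessment records it, the remission must last to Week 12, and that some of these patients might have responded to MT-401 anyway. It is not an estimate of the bias.

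**Conclusion.** The concern holds in limited form. For Group 2 patients other than Arm B crossovers, the written windows allow the pre-dose marrow to precede the last bridging dose by 7 days or more, and a bridging remission can then be counted in the primary CR rate and, in Subgroup C, in ORR. No committed analysis would show it.

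The total bias cannot be computed from the documents. What is firm is 3.3 points per patient per subgroup, against a meaningful gain of more than 10-15 points. Under the assumptions shown, one or two expected misattributions among 30 otherwise non-responding patients (m = 3.3% or 6.7%) raise the chance that an inactive product passes the Table 7 test at a 10% historical rate from 2.6% to 8.6% or 19.4%.

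This is a gap in wording and in pre-specification, cheap to close. It is not evidence that the CR rate will be inflated by a known amount.

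**What to change.** 1. **Protocol.** Reconcile Section 5.1, footnote b and the crossover footnote so that the Baseline disease assessment follows bridging for all Group 2 patients, as is already written for crossovers. In the same edit, reconcile the synopsis (any CR) with Sections 5.1 and 9.1.2 (CR without MRD) on who is analysed separately after bridging. No change to the bridging or washout rules is proposed.

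2. **SAP.** Keep all treated patients in the primary analysis. Add bridging (yes/no) to 7.4.7.1 as a committed factor and report CR, ORR (Subgroup C) and DOCR by bridging status. Prespecify a sensitivity analysis that excludes bridged patients with no marrow after the final bridging dose, or counts them as non-responders.

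Patients without such a marrow should not be moved into the post-bridging remission set. Their remission is unproven, and the move would take treated patients out of the all-treated population because of assessment timing.

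Cost: some marrows must be retimed, a few table rows are added, and estimates by bridging status will be imprecise with 30 per subgroup. A delayed response to bridging after a correctly timed marrow would still be counted. That remains a limitation of the single-arm design and should be stated as one.
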